5.3.8. Tumour Imaging and Assessment of Disease

Tumour response assessments will be carried out by physical examination, and tumour imaging by CT scan and/or MRI. CT scans are the preferred modality for measureable disease unless a participant has a clinical condition e.g. severe contrast allergy, or the lesions are significantly better visualized through the use of an MRI. Tumour response will be assessed based on RECIST v1.1. (See Appendix 4) Baseline lesions must be selected before the start of the treatment. Tumour assessments by CT scan or MRI must be done at 12 weeks, and then 12 weekly thereafter until the end of treatment, progression or withdrawal of the study for any cause. RECIST scans can be performed up to and including 7 days before the participant is due for their next visit to allow the assessment of the scan to be available at the visit.

If no imaging/measurement of the lesion is completed at the requested time point, then the participant cannot be evaluated for progression. If only a subset of the lesions are measured, then this is also considered not evaluable, unless a convincing argument can be made that the contribution of the individual missing lesion(s) would not have changed the assigned time-point response.

Progression of disease should be verified by RECIST 1.1. In cases where progression is equivocal the participant should be re-imaged in 6 weeks. If repeat CT scans or MRI confirm PD, then progression should be declared using the date of the initial scan. If repeat scans do not confirm PD, then the participant is considered not to have progressive disease per RECIST v1.1 and the participant will return to the original imaging schedule. Confirmation of response is not required in these scans. Participants are allowed to continue on treatment beyond progression if there is clinical benefit at investigator's criteria.

Best overall response is determined once the participant has discontinued the study medication. It is defined as the best response designation, as determined by the investigator, recorded between the date of randomisation and the date of objectively documented progression per RECIST v1.1 or the date of subsequent therapy, whichever occurs first. For participants without documented progression or subsequent therapy, all available response designations will contribute to the best overall response assessment. The participant's best overall response assignment will depend on the findings of both target and non-target disease and will also take into consideration the appearance of new lesions. The duration of objective response is measured from the time

measurement criteria are first met for CR or PR (whichever is first recorded) until the first date that PD is objectively documented.

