4.2. Registration

Following the patient's signature of the consent form, this information must be entered into the electronic database which will allocate a unique trial identification number to be used to identify the patient throughout the study. A copy of the consent form must also be faxed to the Trials office to enable source data verification and confirm patient's participation in the study.

NOTE: Sites must alert the trials office to confirm receipt once the consent form has been faxed.

Once all the screening assessments have been completed and the data entered into the eCRFs; the patient will be assessed for eligibility. If eligible, the patient will be randomised into a treatment group. If the patient is not eligible then the local investigator will make alternative arrangements for the treatment of the patient.

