4.3. Randomisation

Patients will be randomised to receive pembrolizumab alone or in combination with radiotherapy. Randomisation will be performed on a 1:1 ratio basis and will be stratified based on the results of;

1. LDH (below or within normal range/above upper limit of the normal range) and
2. previous treatment with anti-CTLA4 agent (yes/no)

Each site will be required to complete all screening eCRFs prior to randomisation to ensure that the eligibility of the patient may be confirmed. Further information regarding randomisation procedures will be provided to sites in the study specific registration and randomisation SOP.

The patients' trial ID will be a unique that once assigned will become the permanent study identifier for that patient. In the event a patient is randomised onto the study but does not begin treatment, then that patient's trial ID will not be reassigned. **Treatment will begin within 3 days from the date of randomisation.** To ensure participant confidentiality, participants will only be identified by their assigned trial ID on eCRFs as well as on other trial specific forms and all communication to RM-CTU. It is the PI's responsibility to maintain a confidential record of the identity i.e. full name, date of birth and hospital number for the participants enrolled in this study and their assigned trial ID. At the end of the study this record should be archived along with the Site File.

PLEASE NOTE: To ensure participant safety, the first participant will be followed **for 6 weeks** or until the resolution of local acute toxicity to grade 1 **before** the second participant may commence treatment.

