4.4. Entry Criteria

4.4.1. Participant Inclusion Criteria

In order to be eligible for participation in this trial, the participant must:

1. Be willing and able to provide written informed consent for the trial.
2. Have a diagnosis of stage III (unresectable) or stage IV cutaneous melanoma or melanoma of unknown primary, as per AJCC staging system.
3. Confirmed metastatic disease by diagnostic biopsy.
4. Be ≥ 18 years of age on day of signing informed consent.
5. Have at least one lesion and a maximum of 3 which are appropriate targets for high dose radiotherapy. This lesion must be 1cm-5cm in size and measurable by RECIST v1.1. The lesions should also be asymptomatic or, in the opinion of the investigator, threaten to become symptomatic.

6. Have in addition at least one other lesion which will not be irradiated but must be measurable by RECIST v1.1 to assess the abscopal effect of the treatment.
7. Have a performance status of 0 or 1 on the ECOG performance scale.
8. Demonstrate adequate organ function as defined in table 1 below. All screening labs should be performed within 7 days of randomisation.

System	Laboratory Value
Haematological	
Absolute neutrophil count (ANC)	≥1,500 /mCL
Platelets	≥100,000 / mCL
Hemoglobin	≥9 g/dL or ≥ 5.6 mmol/L
Renal	
Serum creatinine OR Measured or calculated ^a creatinine clearance (GFR can also be used in place of creatinine or CrCl)	≤1.5 X upper limit of normal (ULN) OR ≥60 mL/min for participant with creatinine levels > 1.5 X institutional ULN
^a Creatinine clearance should be calculated per institutional standard.	
Hepatic	
Serum total bilirubin OR Direct bilirubin	≤ 1.5 X ULN OR ≤ ULN for participants with total bilirubin levels > 1.5 ULN
AST (SGOT) and ALT (SGPT)	≤ 2.5 X ULN OR ≤ 5 X ULN for participants with liver metastases
Coagulation	
Prothrombin Time (PT)	≤1.5 X ULN unless participant is receiving anticoagulant therapy as long as PT or PTT is within therapeutic range of intended use of anticoagulants
Activated Partial Thromboplastin Time (aPTT)	≤1.5 X ULN unless participant is receiving anticoagulant therapy as long as PT or PTT is within therapeutic range of intended use of anticoagulants

Table 2: Adequate Organ Laboratory Values

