6.2.2. Sites suitable for radiotherapy

Participants must have at least two sites of metastatic disease from their primary melanoma. One of the metastatic sites will serve as the index lesion for subsequent assessment of the abscopal effect and should not receive RT. A maximum of 3 Lesion(s) can be irradiated and must be at least 1 cm but no more than 5 cm in size, as measured by its widest dimension on CT scan (for internal lesions) or on clinical inspection (for superficial lesions). Metastatic lesions must not be an intra-cranial, intra-ocular lesion or intra-mesenteric lesion to receive RT. The choice of the lesion(s) to be irradiated will be left to the discretion of the attending oncologist, taking into account the Organs At Risk (OAR) normal tissue tolerance constraints associated with irradiating each lesion, and importantly the ease of obtaining pre and post radiotherapy biopsies from the index lesion(s) for the associated translational study. For example, if there is one internal and one superficial

² Patients will be consented to allowing their images to be sent outside of their institution. Please refer to the current Radiotherapy Imaging Manual for further guidance

³ Further information on this section is available in the current Radiotherapy QA Guidelines Manual which will be provided by the trials office

lesion, it may be preferable to irradiate the internal lesion so that biopsy can be taken from the superficial lesion pre and post irradiation.

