6.3.10. Trial Blinding/Masking

This is an open-label trial; therefore, the Sponsor, investigator and participant will know the treatment being administered.

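### RECIST baseline lesions may be chosen after open-label randomisation, and the irradiated and index lesions need not be named beforehand in either arm

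*Combined protocol and SAP*

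**What the plan says.** **RECIST baseline lesions.** Protocol 5.3.8: "Baseline lesions must be selected before the start of the treatment". This is the only timing rule for choosing them.

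**Interval after allocation.** Section 4.3: "Treatment will begin within 3 days from the date of randomisation". Under 6.3.10, "the Sponsor, investigator and participant will know the treatment being administered".

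**Eligibility.** Inclusion criterion 5 (4.4.1): "Have at least one lesion and a maximum of 3 which are appropriate targets for high dose radiotherapy". Criterion 6 asks for a further RECIST-measurable lesion, left without radiotherapy, on which an abscopal response can be judged. Both are settled before allocation. Section 4.2 puts the eligibility assessment first ("If eligible, the patient will be randomised into a treatment group"), and 4.3 adds "Each site will be required to complete all screening eCRFs prior to randomisation to ensure that the eligibility of the patient may be confirmed".

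**Irradiated and index lesions.** Section 6.2.2: "The choice of the lesion(s) to be irradiated will be left to the discretion of the attending oncologist". Under 6.1 and 6.2.2 at least one lesion is left un-irradiated as the index lesion for the abscopal effect. Radiotherapy falls between pembrolizumab doses 1 and 2 (6.2.1). No section gives a deadline for naming either lesion or asks for them to be named in the pembrolizumab-alone arm.

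**Use of the lesions.** The primary endpoint is patient-level CR or PR by RECIST 1.1 at 12 weeks in all randomised patients (8.4.1, 8.4.2). Response in non-irradiated lesions is a secondary objective (2.1.2).

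**The concern.** Other screening steps are timed against randomisation: laboratory tests within 7 days and the pregnancy test within 72 hours (4.4.1). Lesion selection is timed against the start of treatment, which comes later and when the arm is known.

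Two separate things are at stake.

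1. **The primary comparison.** Lesions suitable for radiotherapy must themselves be RECIST-measurable (criterion 5), and nothing bars them from the RECIST target set. An investigator who knows the arm can decide whether a lesion due for radiotherapy enters the target sum, or can favour lesions thought likelier to shrink. Section 5.3.8 names the investigator as assessor for best overall response. The only central image review described (6.1) is by the Radiotherapy QA team and is not presented as a blinded RECIST reading.

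2. **The abscopal question.** The index lesion exists as a designated lesion only where radiotherapy is given. A like-for-like comparison of non-irradiated lesions between arms then needs a control set chosen afterwards.

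**Working it through.** **Step 1. Timing, lesion by lesion**

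| Lesion decision | Latest time the text allows | Can the arm be known? |
|---|---|---|
| Qualifying lesions exist (criteria 5 and 6) | Before randomisation (4.2, 4.3) | No |
| RECIST baseline lesions selected | Before treatment starts, up to 3 days after randomisation (5.3.8, 4.3) | Yes |
| Lesion(s) to irradiate named | No deadline; radiotherapy follows dose 1 (6.2.1, 6.2.2) | Yes |
| Index lesion named, radiotherapy arm | No deadline (6.1, 6.2.2) | Yes |
| Would-be irradiated and index lesions named, control arm | Not asked for | Not applicable |

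**Step 2. The plan's sample size (8.2)**

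Inputs: 30% against 50%, two-sided 5%, power 80%, dropout 10%. The mean rate is 0.40.

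- Without continuity correction: n = [1.960 × √(2 × 0.40 × 0.60) + 0.842 × √(0.30 × 0.70 + 0.50 × 0.50)]² / 0.20² = 93 per arm.
- With continuity correction: (93/4) × [1 + √(1 + 4/(93 × 0.20))]² = 102.8, so 103 per arm. The plan states 105, which is within 2 patients.
- Dropout: 210 / 0.9 = 233.3, so 234, or 117 per arm.

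The stated size reproduces closely, and nothing in this point changes it.

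**Step 3. What an arm-dependent choice could do to the primary test**

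The documents give no figure for the shift, so it is assumed. Let the true response rate be 30% in both arms, and let lesion choice add s percentage points in the radiotherapy arm only. The test is the uncorrected chi-squared test, with Z = |a − b|/n ÷ √(2p̂(1 − p̂)/n), where a and b are the responders in the two arms and p̂ is the pooled rate. It is significant when Z > 1.960. The probability below sums Bin(n, 0.30) × Bin(n, 0.30 + s) over all significant tables that favour radiotherapy.

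| Assumed s (points) | Patients affected out of 117 | False positive favouring radiotherapy, 105 per arm | Same, 117 per arm |
|---|---|---|---|
| 0 | 0 | 2.5% | 2.5% |
| 3 | 3.5 | 6.7% | 7.1% |
| 5 | 5.9 | 11.6% | 12.6% |
| 10 | 11.7 | 33.3% | 35.9% |

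The 117 column matches the intention-to-treat population; 105 is the planned number before dropout. The table shows how sensitive the test is to a small one-sided shift. It does not estimate the shift.

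**Step 4. Whether the missing control designation reaches the primary endpoint**

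The primary analysis compares patient-level CR or PR rates (8.5) and does not use the index lesion, so it is not reached. The planned lesion-level test is McNemar's test within patients between time points (8.5), and no between-arm test of non-irradiated lesions is specified. The gap bears on the secondary objective in 2.1.2.

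**The case against.** The best case for the plan is that tumour imaging is a screening assessment (schedule in 5.1), and screening data must be entered before eligibility is assessed and the patient randomised (4.2, 4.3). Criterion 5 sets a size range, so at least one lesion has to be measured by then. In practice baseline lesions may already be on the eCRF at allocation. The eCRF and the randomisation SOP are not among the documents, so this cannot be ruled out. What stands is that the protocol does not require it and 5.3.8 sets a later deadline. Lesion choice also does not wholly determine response: non-target disease and new lesions count too (5.3.8, stated for best overall response).

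A reader might infer more than the text supports:

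- *That entry to the trial can depend on the arm.* It cannot by this route, because both lesion criteria are confirmed before randomisation.
- *That the radiotherapy target falls under the start-of-treatment deadline.* Section 5.3.8 covers baseline lesions only; the radiotherapy target has no stated deadline.
- *That undesignated control lesions bias the primary endpoint.* They do not, as step 4 shows.
- *That the gap is beyond later repair.* Sites must keep original images (10.4), so a blinded reader could choose lesions from baseline scans in both arms. Repair would be partial: response also uses physical examination (5.3.8), and 6.2.3 expects most irradiated metastases to be in skin and superficial nodes.

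**Conclusion.** The concern holds in two parts. First, the protocol permits RECIST target lesions to be chosen for up to 3 days with the arm known, and this could bias the 12-week response comparison by an unknown amount. Second, the irradiated and index lesions have no naming deadline and no control-arm counterpart, so a between-arm comparison of non-irradiated lesions lacks a prospectively defined control set.

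The timing conclusion rests on the text alone. The false-positive figures rest on assumed shifts of 3, 5 and 10 points, all in one direction, and should not be read as the likely size. This should be fixed. It is not a defect that invalidates the design, since screening practice may already close part of the gap and some of it can be rebuilt from retained scans.

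**What to change.** 1. In 5.3.8, make randomisation, not the start of treatment, the deadline for selecting baseline lesions.
2. In 4.3, require the screening eCRF to record, for every patient in both arms and before the allocation is released: (a) RECIST target and non-target lesions; (b) the lesion(s) that would be irradiated if so allocated; (c) the lesion(s) that would not be.
3. Keep the RECIST set fixed after allocation. If the lesion actually irradiated differs from the one designated, record the change and the reason.
4. For the analysis of non-irradiated lesions, use the pre-designated index lesions in both arms. Add a sensitivity analysis that excludes any designated index lesion that was in fact irradiated. Without such a rule, an irradiated lesion could be counted as un-irradiated; the prospective radiotherapy plan review (6.2.4.4) makes changes of target foreseeable.

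The cost is one wording change, a few eCRF fields and a short analysis rule. The small downside is that lesions must also be nominated at screening for patients who will be controls, although criteria 5 and 6 already require sites to establish that such lesions exist. No extra scan is needed, and sample size, alpha and power do not change.

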2.2.2 Secondary Endpoints

- To determine response rates by RECIST v1.1 at 6 months post treatment
- To measure individual lesion response assessment every 12 weeks taking account of within patient data
- To assess the toxicity of the combination of pembrolizumab and high dose radiotherapy after 12 weeks of treatment.
- To assess PFS at 1, 2 and 3 years post treatment.
- To assess OS in the arms of the study.

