5.2.5. Survival Status

The investigator or qualified designee will assess the participant for survival status at specified visits as defined in the schedule of study assessment (Table 2) The assessment will include the participant status, details of anti-cancer treatments administered and if applicable details of participant death or details if participant has been lost to follow-up.

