6.4.2. Prohibited Concomitant Medications

Participants are prohibited from receiving the following therapies during the screening and treatment phase (including retreatment for post-complete response relapse) of this trial:

- Anti-cancer systemic chemotherapy or biological therapy
- Immunotherapy not specified in this protocol
- Radiotherapy not specified in this protocol
- Investigational agents other than pembrolizumab
- Palliative radiotherapy for symptom control
- Live vaccines within 30 days prior to the first dose of trial treatment and while participating in the trial.

Examples of live vaccines include, but are not limited to, the following: measles, mumps, rubella, chicken pox, yellow fever, rabies, BCG, and typhoid (oral) vaccine. Seasonal influenza vaccines for injection are generally killed virus vaccines and are allowed; however intranasal influenza vaccines (e.g. Flu-Mist®) are live attenuated vaccines, and are not allowed.

- Glucocorticoids for any purpose other than to modulate symptoms from an event of clinical interest of suspected immunologic etiology. The use of physiologic doses of corticosteroids may be approved after consultation with the CI/designee.

Participants who, in the assessment by the investigator, require the use of any of the aforementioned treatments for clinical management should be removed from the trial. Participants may receive other medications that the investigator deems to be medically necessary. The Exclusion Criteria describes other medications which are prohibited in this trial. There are no prohibited therapies during the Post-Treatment Follow-up Phase.

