6.11. Withdrawal from the Study

Withdrawal from the study refers to discontinuation of both trial medication and future study visits / assessments; this can occur at any time according to the following reasons:

- Patient decision
- Lost to follow-up
- Death
- PI decision

Subjects may withdraw consent at any time for any reason or be dropped from the trial at the discretion of the investigator should any untoward effect occur. In addition, a patient may be withdrawn by the investigator if enrolment into the trial is inappropriate, the trial plan is violated, or for administrative and/or other safety reasons. When a patient discontinues/withdraws prior to trial completion, all applicable activities scheduled for the final trial visit should be performed at the time of discontinuation. Any adverse events which are present at that time should be followed in accordance with the safety requirements outlined in Section 7. Patients who a) attain a CR or b) complete 24 months of treatment with pembrolizumab may discontinue treatment with the option of restarting treatment dependant on the investigators clinical judgement. After discontinuing treatment following assessment of CR, these patients should return to the site for a safety follow-up visit and then proceed to the survival follow-up period of the study as described in the schedule of study assessments (Table 2).

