8.2. Sample Size and Power Considerations

The sample size of this study was calculated using a 2-sided α of 5%; power of 80%; RECIST response rate in the pembrolizumab arm is 30%; RECIST response rate in the pembrolizumab and radiotherapy arm is 50%. The study will randomise 234 patients in total (210 minimally required for statistical power calculation purposes, 105 patients in each arm; 20 additional patients to account for potential drop outs – an expected drop out rate of 10%) over 18 months i.e. 11-12 patients per month in approximately 15 to 24 UK centres. In the event that enrolment is slower than expected the Trial Steering Committee will consider adding additional UK sites. Patients enrolled in the trial are expected to be recruited from the routine clinics of the participating centres.

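### Scheduled tumour imaging ends with treatment, so progression after a stop without progression is not systematically recorded and PFS at 1 to 3 years is open to bias in either direction

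*Combined protocol and SAP*

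**What the plan says.** **Imaging.** Section 5.3.8: "Tumour assessments by CT scan or MRI must be done at 12 weeks, and then 12 weekly thereafter until the end of treatment" (sooner if the patient withdraws or progresses). Table 3 shows no tumour imaging at the safety or survival follow-up. Its footnotes add one end-of-treatment scan, only if no RECIST assessment was done in the previous 6 weeks. They also limit the end-of-treatment visit to patients who come off treatment between cycles.

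**After treatment.** Section 5.1 sends everyone who permanently stops to a 30-day safety visit and then to 12-weekly survival follow-up. Section 6.11 says of patients who stop after a complete response: "these patients should return to the site for a safety follow-up visit and then proceed to the survival follow-up period of the study". Section 6.9, however, ties entry to that phase to confirmed progression or a new anti-cancer therapy.

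**Content of survival follow-up.** Section 5.2.5: "The assessment will include the participant status, details of anti-cancer treatments administered and if applicable details of participant death", or loss to follow-up. Under Section 6.9 there are no clinic visits; information comes from the medical notes, the GP or the telephone.

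**Removal.** Section 6.4.2 says that participants who, in the investigator's assessment, "require the use of any of the aforementioned treatments for clinical management should be removed from the trial". The list includes palliative radiotherapy and most glucocorticoid use. Section 6.6.3 uses similar wording for pregnancy.

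**Endpoints.** Section 2.2.2: "To assess PFS at 1, 2 and 3 years post treatment". Section 8.4.2 counts PFS from treatment start to progression or death from any cause. It censors living patients without progression at the 1-, 2- and 3-year points, and those lost or withdrawn at their last assessment. Section 8.4.1 promises intention-to-treat analysis of response, PFS and OS.

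**The concern.** PFS needs progression to be looked for in the same way until the event or the analysis time. Here the search stops when treatment stops, and stopping is related to prognosis: complete responders are doing best, and patients with toxicity may differ from the rest in either direction. Section 8.4.2 has no explicit rule for a patient who is alive, off treatment, not known to have progressed and no longer scanned. Such a patient may be censored at the last scan or counted as progression-free to the landmark, and the two choices push the estimate in opposite directions. Progression dates that were never collected may not be recoverable at analysis.

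The primary endpoint has a narrower exposure. A patient who stops or is removed before week 12 may have no week-12 scan, and Sections 8.4.1 to 8.5 do not say how a missing response is counted.

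**Working it through.** **1. Which stop affects which endpoint**

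The first scheduled scan on study is at week 12.

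| Reason for stopping | Week-12 response | PFS |
|---|---|---|
| Toxicity or removal before week 12 | At risk | At risk from the stop onward |
| Toxicity after week 12 | Not affected | At risk from the stop onward |
| Complete response seen on a scheduled scan | Not affected: the scan that shows it is at week 12 or later | At risk from the stop onward |
| 24 months completed | Not affected | Essentially 3-year PFS only: no scan is scheduled in months 24 to 36 |

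The end-of-treatment scan does not close the gap. It is a single conditional scan, and before week 12 it is not a week-12 assessment. Screening may fall up to 28 days before the first dose, so if the baseline scan counts towards the 6-week condition, a very early stopper may have no post-baseline scan.

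**2. 3-year PFS under the two readings**

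The documents give no complete-response or stopping rates by arm, so these inputs are assumptions: complete response in 20% (radiotherapy arm) v 10% (control); all complete responders stop at month 6, none having progressed; 90% of them are progression-free at 3 years; all other patients have exponential PFS reaching 20% at 36 months and are scanned throughout.

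- Hazard in the others: −ln(0.20)/36 = 0.0447 per month, so S(6) = exp(−0.268) = 0.765.
- Truth: 0.20×0.90 + 0.80×0.20 = 34%; 0.10×0.90 + 0.90×0.20 = 27%. Difference 7 points.
- Censored at last scan (month 6): Kaplan-Meier at 36 months = [CR + (1−CR)×0.765] × (0.20/0.765), giving 21.2% and 20.6%. Difference 0.6 points.
- Carried progression-free to the landmark: 0.20 + 0.80×0.20 = 36%; 0.10 + 0.90×0.20 = 28%. Difference 8 points.

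A second set of assumptions gives the same two-way pattern. Suppose 15% are complete responders who stop at 6 to 12 months, with a median PFS of 60 months against 7 months in the rest. True 2-year PFS is 19.3%. Censoring at the stop gives about 11.1%; carrying to the landmark gives about 21.4%. With 5% complete responders the figures are 12.5%, 9.8% and 13.3%.

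**3. Primary endpoint**

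The design figure reproduces closely. For 30% v 50%, two-sided 5% and 80% power (Section 8.2), the two-proportion formula with continuity correction gives 103 per arm against the stated 105, and 210/0.90 = 233.3, rounded up to 234.

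If a share m of patients has no week-12 scan and is counted as non-responding, the observed rate is p(1−m). With n = 117 per arm and an uncorrected chi-squared test, power = Φ{[|p₂−p₁|√n − 1.96√(2p̄(1−p̄))] / √[p₁(1−p₁)+p₂(1−p₂)]}. The missing shares are assumptions.

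| Missing, control / radiotherapy | Observed rates | Power |
|---|---|---|
| 0 / 0 | 30% v 50% | 88.2% |
| 5% / 5% | 28.5% v 47.5% | 85.4% |
| 10% / 10% | 27% v 45% | 82.2% |
| 15% / 15% | 25.5% v 42.5% | 78.8% |
| 5% / 10% | 28.5% v 45% | 74.8% |

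Equal missingness up to the planned 10% leaves power above 80%. Unequal missingness would cost more, but nothing in the documents shows that it will occur.

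**The case against.** The strongest reply is that PFS is only partly missing. Deaths are PFS events and remain captured. Stopping for complete response or at 24 months is optional, and treatment may be restarted. Survival follow-up already draws on the medical notes, where routine scans may be found. All of this stands and reduces the size of the problem. It does not remove it, because Section 5.2.5 does not ask for progression and no section creates an off-treatment imaging phase. The instruction in Table 3 to scan regardless of delays concerns delayed cycles, not discontinuation.

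Some stronger readings are tempting but not supported:

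- A reader might infer that week-12 response is lost for patients who stop for complete response or at 24 months. The timing rules this out. Early stoppers are not dropped from the primary analysis either: Section 8.4.1 keeps all randomised patients in the denominator.
- A reader might infer that the plan will shrink a real PFS benefit to almost nothing. That requires last-scan censoring, which Section 8.4.2 states only for patients lost or withdrawn. Read literally, it carries other living patients without recorded progression to the landmark, and the difference is then slightly overstated.
- A reader might infer that missingness will differ by arm. That is possible: added toxicity could produce more stops with radiotherapy, and palliative radiotherapy more removals in control. Neither is shown.
- A reader might take the removal wording in Section 6.4.2 to mean that all data collection ends. Section 6.4 speaks only of possible discontinuation from trial therapy, Section 6.9 sends patients starting new anti-cancer therapy to survival follow-up, and Sections 6.10.1 and 6.11 separate stopping medication from study withdrawal. The wording is loose and needs reconciling; it does not establish loss of data.

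**Conclusion.** The point holds for PFS after a stop without progression. Followed as written, the plan does not systematically capture progression in these patients, and Section 8.4.2 leaves their censoring open. A stop for toxicity or complete response affects later PFS; a 24-month stop affects essentially only the 3-year figure.

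The true size cannot be derived from the documents. In the first illustration a 7-point difference is reported as 0.6 or 8 points, depending only on the censoring rule. Both distortions rest on assumed rates and shrink as fewer complete responders stop.

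For the primary endpoint the exposure is limited to stops or removals before week 12, and no arm difference is demonstrated. This should be fixed, mainly for a secondary endpoint of a phase II trial powered on week-12 response; it does not undermine the primary analysis.

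**What to change.** 1. **Survival eCRF.** Add the date and result of the latest scan and the date of progression to the 12-weekly contact, taken from the notes already being reviewed under Section 6.9.
2. **Section 5.3.8 and Table 3.** Keep the 12-weekly RECIST assessment, including week 12, for patients who stop treatment without progression, using routine scans where these are done, until progression, new anti-cancer therapy, death or withdrawal of consent. Reconcile Sections 5.1, 6.9 and 6.11 on who enters survival follow-up and when.
3. **Section 8.4.2.** State one censoring rule for patients who stop without progression: censoring at the last adequate tumour assessment, with a sensitivity analysis that carries them to the landmark. State how new anti-cancer therapy is handled.
4. **Sections 6.4.2 and 6.6.3.** Separate leaving trial treatment from leaving the study, so that only withdrawal of consent, loss to follow-up or death ends data collection. This concerns data collection only and leaves the treatment rules as they are.

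The cost is amendment wording, a few eCRF fields and a little more data collection. The sample size stays at 234. Item 2 is the costlier part, because it adds scans where a site would not image off-treatment patients routinely. Items 1, 3 and 4 are worth making even if item 2 is limited to routine scans.
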